**c) Study Endpoints\***

i) **Primary endpoints:** Blood pressure readings in mm/Hg and heart rate in beats per minute (bpm)

(1) According to the American Heart Association, blood pressure readings are as follows:

(a) Normal: Less than 120/80mmHg

(b) Elevated: 120-129/<80 mmHg

(c) Stage I Hypertension: 130-139/80-89 mmHg

(d) Stage II Hypertension: >140/>90 mmHg

(e) Hypertensive Crisis: >180/>120 mmHg

ii) **Primary safety endpoints:** Adverse events will be recorded for both *Passiflora incarnata* extract and the audio-guided meditation

**d) Procedures involved in the Human Research\***

i) This will be a randomized, double-blind, placebo controlled trial.

ii) Students will be randomized to Group I, II, or III before the study begins

UB HRP-503 TEMPLATE: Protocol

PROTOCOL TITLE: Investigating the short-term effects of *Passiflora incarnata* and mobile audio-guided meditation on blood pressure and heart rate in naturopathic medical students

PROTOCOL DATE: 3/28/19

Template Revised: June 14, 2010

- iii) Naturopathic medical students will come to the study area in groups of 15-25 (each naturopathic cohort will be studied on a different day)
- iv) Naturopathic medical students will be studied on the day of a classroom examination with three left arm seated blood pressure readings and one heart rate reading taken 15 minutes after the end of the exam and then 15 minutes after that.
- v) All participants will be instructed to download Headspace app onto their smartphone prior to the research date
- vi) The participants will be randomized into three groups
  - (1) Group I
    - (a) Baseline (15 minutes post-exam) blood pressure readings (three left arm seated readings, average will be calculated) and one heart rate reading taken after at least 5 minutes of rest time without talking, eating, or caffeine consumption.
    - (b) This group will not be given any intervention. Subjects will sit quietly for 15 minutes and can read a book, surf the internet, etc. Subjects may not consume caffeine, eat food, or listen to any meditation during this time.
    - (c) Three left arm seated blood pressure readings and one heart rate will be taken 15 minutes after the baseline reading.
  - (2) Group II
    - (a) Baseline (15 minutes post-exam) blood pressure readings (three left arm seated readings, average will be calculated) and one heart rate reading taken after at least 5 minutes of rest time without talking, eating food, or caffeine consumption.
    - (b) 15 minutes after classroom examination – will be given 1/4 tsp of blackstrap molasses placebo and a 10 minute audio-guided mobile meditation session via the Headspace App. Subjects may not consume caffeine or eat food during this time.
    - (c) Three left arm seated blood pressure readings and one heart rate will be taken 15 minutes after the baseline reading.
  - (3) Group III
    - (a) Baseline (15 minutes post-exam) blood pressure readings (three left arm seated readings, average will be calculated) and one heart rate reading taken after at least 5 minutes of rest time without talking, eating, or caffeine consumption.
    - (b) 15 minutes after examination – will be given 1/8 tsp (900mg) of *Passiflora incarnata* solid extract by Wise Woman Herbals mixed with 1/8 tsp of blackstrap molasses to mask the taste and a 10 minute audio-guided mobile meditation session via the Headspace App. Subjects may not consume caffeine or eat food during this time.
    - (c) Three left arm seated blood pressure readings and one heart rate will be taken 15 minutes after the baseline reading.

UB HRP-503 TEMPLATE: Protocol

PROTOCOL TITLE: Investigating the short-term effects of *Passiflora incarnata* and mobile audio-guided meditation on blood pressure and heart rate in naturopathic medical students

PROTOCOL DATE: 3/28/19

Template Revised: June 14, 2010

vii) Safety considerations

- (1) All participants will be given a paper survey about adverse events (*see Attachment C*) which will be returned to the research team by the end of the same study day. Any participant who marks a moderate-severe adverse event will be followed up by [name] for appropriate management.
- (2) [name] phone number and contact information will be given to the study subjects so they can contact her in the event another adverse event arises after the survey has been returned.
- (3) The research will last for about 45 minutes. Three Blood pressure readings (all left arm seated) and one heart rate reading will be taken at baseline and again 15 minutes later.
- (4) Procedures taken to lessen the probability or magnitude of risks
  - (a) Adverse events related to *Passiflora incarnata* use have been found with chronic dosage. We attempt to minimize these risks by providing one-time acute dosage.
  - (b) We are attempting to minimize adverse events by excluding participants who are taking hypertensive medication, anti-anxiety medication, MAOI medication, or blood-thinning medication.
  - (c) We are attempting to minimize adverse events by excluding participants who are pregnant or may be pregnant.
  - (d) We are attempting to minimize adverse events by excluding participants who recently consumed cold medicine, cough suppressants, decongestant medication, antihistamine medication, stimulant medication, or tyramine containing foods to avoid interaction with *Passiflora incarnata*.
- (5) Initial data collected from the subjects
  - (a) The inclusion/exclusion criteria data will be collected from the participants before the start of the research (*see Attachment B*). This data will be collected in private with [name] or [name].
  - (b) Age, sex, significant past medical history (previous diagnoses), and medication usage. This information will be gathered via questionnaire (*see Attachment D*) before the start of the research. This data will be collected in private with [name] or [name].
  - (c) Adverse event survey will be collected from the participants by the end of the research day (*see Attachment C*)

e) **Data management\***

- i) Participants will be assigned a de-identifying code upon participation in the research
- ii) This code will be used to randomize the participants into Group I, II, and III
- iii) This code will be placed on both their initial questionnaire, inclusion/exclusion checklist, BP and HR readings, and their adverse events survey

UB HRP-503 TEMPLATE: Protocol

PROTOCOL TITLE: Investigating the short-term effects of *Passiflora incarnata* and mobile audio-guided meditation on blood pressure and heart rate in naturopathic medical students

PROTOCOL DATE: 3/28/19

Template Revised: June 14, 2010

- iv) This code will be linked with the participants' baseline and 15-minute blood pressure readings
  - v) A master sheet linking the code back to the subject's name will be stored on the password-protected University laptop belonging to only the co-investigators in a password-protected Excel sheet.
    - (1) This master sheet will not be printed or emailed between investigators.
  - vi) Hard copies of the inclusion/exclusion criteria checklist, the initial data questionnaire, BP and HR readings, and the adverse event survey will be stored in a locked file cabinet in the primary investigator's office. These forms will be shredded after three years.
  - vii) Power analysis – 45-60 subjects are needed to obtain 80%-90% power, respectively
  - viii) Data analysis will be done by our student research assistants and [name]
- f) Provisions to monitor the data for the safety of subjects\***
- i) [name] will evaluate the adverse events survey and follow up with any participant who experience a moderate-severe adverse event
  - ii) Participants will be encouraged to report additional adverse events to [name] directly in the days following the research even once the survey has been handed in.
- g) Withdrawal of subjects\***
- i) Participants can voluntarily withdraw at any time
  - ii) Once a participant has withdrawn from the research, his/her data will not be included in our analysis
  - iii) Withdrawal may occur without the participants' consent if:
    - (1) His/Her smartphone or Headspace application is not functioning within 30 minutes after the end of his/her classroom examination
    - (2) He/She did not take the classroom examination that day
    - (3) He/She eats food/tyramine containing food, stimulant medication, alcoholic beverages, cold medicine, decongestant medication, antihistamine medication, cough suppressant medication, stimulant energy drinks, or consume caffeine within 2 hours before the study period or during the study period.
- 7) Risks to subjects\***
- a) Privacy Risks**
- i) Since naturopathic medical students will be studied in groups in one large room, the subjects will be informed that his/her classmates in the same room will know that he/she is participating in the study.
  - b) To minimize any privacy risks, all medical information will be collected in private before the day of the study. On the day of the study, we will not read the participants' blood pressure and heart rate readings out loud. We also will ask the participant to write down what medications or drinks taken on the day of the study

UB HRP-503 TEMPLATE: Protocol

PROTOCOL TITLE: Investigating the short-term effects of *Passiflora incarnata* and mobile audio-guided meditation on blood pressure and heart rate in naturopathic medical students

PROTOCOL DATE: 3/28/19

Template Revised: June 14, 2010

so that the participant does not have to say this information out loud in order to protect privacy.

- c) **Inconveniences: Time Invested/Timing with Classroom Examination**
  - i) The participants may be inconvenienced by sparing 45 minutes after his/her classroom examination
  - ii) The participant may feel distracted during his/her examination in anticipation of the research taking place after the examination
    - (1) This is unlikely, as the research is intended to have a relaxing benefit on the participant
  - iii) The participant may be late to his/her next class by participating in the research
    - (1) This may be unforeseeable and may be likely. However, the research period will last only 45 minutes.
  - iv) The subject may not eat any food/tyramine containing foods or consume caffeine, cold medicine, cough suppressant medication, antihistamine medication, decongestant medication, alcoholic beverages, stimulant medications, or stimulant energy drinks for 2 hours before the study period or during the study period, which might inconvenience the student
- d) **Blood Pressure Reading**
  - i) Participants may feel a slight discomfort when the blood pressure cuff is tightened around his/her arm. This is a temporary sensation that will last no more than 1 minute on each occasion.
- e) **Audio-Guided Mobile Meditation Application**
  - i) The participant may be inconvenienced by having to download the Headspace application onto his/her smartphone
    - (1) This should be a minor inconvenience, as detailed instructions will be provided ahead of time (*see Attachment E*)
  - ii) The participant may use data or wifi on his/her smartphone by downloading and utilizing the Headspace application
    - (1) This is an unforeseeable risk, as everyone's cellular data plan is different. Participants will be encouraged to connect to wifi to download and use the application to avoid accruing data usage charges (*see Attachment E*)
  - iii) The participant may have to purchase headphones to listen to the Headspace meditation on his/her smartphone if he/she does not already own them
    - (1) This is unlikely, as most students already own headphones
  - iv) There are no known serious adverse effects related to meditation
    - (1) An unforeseeable adverse effect is possible, but unlikely, according to existing literature.
- f) ***Passiflora incarnata* extract**
  - i) Some participants may dislike the flavor of the *Passiflora incarnata* extract (mixed with molasses to hide the taste) or the blackstrap molasses placebo
  - ii) Studies on *Passiflora incarnata* have generally found mild-moderate adverse effects when taken for weeks-months including:

UB HRP-503 TEMPLATE: Protocol

PROTOCOL TITLE: Investigating the short-term effects of *Passiflora incarnata* and mobile audio-guided meditation on blood pressure and heart rate in naturopathic medical students

PROTOCOL DATE: 3/28/19

Template Revised: June 14, 2010

- (1) Drowsiness (very common, up to 50% reported this adverse effect in studies). Due to this very common side effect, we advise the subject to exercise caution and avoid operating a vehicle or heavy machinery for one hour after taking the dose.
- (2) Muscle relaxation (common, up to 20% reported this in studies). Due to this very common side effect, we advise the subject to exercise caution and avoid operating a vehicle or heavy machinery for one hour after taking the dose.
- (3) Dizziness (common, up to 5% reported this in studies). Due to this very common side effect, we advise the subject to exercise caution and avoid operating a vehicle or heavy machinery for one hour after taking the dose
- (4) Headache
- (5) Abdominal Pain
- (6) Flatulence
- (7) Vasculitis (rare)
- (8) Asthma
- (9) Rhinitis
- (10) Urticaria/Allergic Reaction
- (11) Cardiovascular effects, including Ventricular Tachycardia (one case study, rare)
- (12) Uterine contractions
- (13) Nosebleed, blood-thinning
- (14) Impairment of Job Performance
- (15) Confusion
- (16) Ataxia
- (17) Other unforeseeable adverse reactions

iii) Our exclusion criteria is intended to reduce the risk of adverse events. Our study will involve a one-time acute dosing of *Passiflora incarnata* to reduce the risk of adverse events from chronic, long-term usage.

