### 2) Objectives\*

This study is intended to study the effects of one-time acute dosing of a solid extract of *Passiflora incarnata*, also known as Passionflower, along with a 10 minute audio-guided mobile meditation on medical students after a didactic examination. Our hypothesis is that blood pressure levels and heart rates, as an assessment of sympathetic tone, will decrease significantly in response to both *Passiflora incarnata* and the meditation.

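### Protocol 6(d)(i) calls the whole trial double-blind and placebo controlled, but that can hold only for Group III vs Group II, where meditation does not differ

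*Protocol*

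**What the plan says.** The design statement in Protocol Section 6(d)(i) covers the trial as a whole: "This will be a randomized, double-blind, placebo controlled trial." The hypothesis in Section 2 expects blood pressure and heart rate to fall "in response to both *Passiflora incarnata* and the meditation".

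Section 6(d)(vi) then fixes three arms:

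- **Group I:** "This group will not be given any intervention." Participants sit quietly and may read or go online, with this limit: "Subjects may not consume caffeine, eat food, or listen to any meditation during this time."
- **Group II:** each participant "will be given 1/4 tsp of blackstrap molasses placebo and a 10 minute audio-guided mobile meditation session".
- **Group III:** Passiflora extract, "mixed with 1/8 tsp of blackstrap molasses to mask the taste and a 10 minute audio-guided mobile meditation session via the Headspace App".

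Section 6(d)(v) has every participant download the meditation app beforehand. Section 7(a)(i) describes the setting: "Since naturopathic medical students will be studied in groups in one large room".

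**The concern.** Double-blind and placebo controlled are properties of a comparison, and a three-arm trial has three of them. Group I has no placebo and no sham session. Its participants have installed the app, are given nothing to swallow, are told not to meditate, and sit with classmates studied at the same session. They cannot be unaware that they are in the untreated arm.

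Group I is also the only arm without meditation, so anything the trial says about meditation has to come from a comparison with it. As written, 6(d)(i) gives those comparisons a protection they lack. A lower follow-up reading in Group II than in Group I could reflect the meditation, the act of taking something, the expectation that goes with being treated, or a mixture. A reader relying on 6(d)(i) would think the last two had been controlled.

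**Working it through.** The point concerns the structure of the arms, so the main check is to set the arms side by side. The protocol's sample-size figures play no part beyond giving the counts in step 3.

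**Step 1. What differs in each comparison** (inputs: Sections 6(d)(i) and 6(d)(vi)).

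| Comparison | What differs | Placebo on the control side? | Can participants be blind? | Does meditation differ? |
|---|---|---|---|---|
| III vs II | Passiflora in molasses vs molasses alone | Yes | Yes | No |
| II vs I | Meditation, molasses, awareness of treatment | No | No | Yes |
| III vs I | Passiflora, molasses, meditation, awareness of treatment | No | No | Yes |

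In III vs II the nominal volumes match: 1/8 + 1/8 = 1/4 tsp in Group III against 1/4 tsp in Group II. Molasses masks the taste and the meditation is the same, so the 6(d)(i) description can apply there.

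**Step 2. Count.** Three groups give 3 pairwise comparisons. Two involve Group I, and these are the same two in which meditation differs. The description can therefore fit 1 of 3 comparisons, and 0 of the 2 that bear on meditation.

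**Step 3. Participants involved.** Totals of 45, 60 and 70 come from Sections 6(b)(iv) and 6(e)(vii). No allocation ratio is given, so equal arms are assumed.

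| Total | Group I (total / 3) | Groups II + III |
|---|---|---|
| 45 | 15 | 30 |
| 60 | 20 | 40 |
| 70 | 23.3 | 46.7 |

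Sessions take 15 to 25 students (Section 6(d)(iii)). If arms are also equal within a session, Group I has 15/3 = 5 to 25/3 = 8.3 participants, alongside 10 to 16.7 who take a spoonful and meditate.

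**Step 4. Does the reading of the hypothesis matter?** If Section 2 means two separate effects, the meditation effect rests on II vs I. If it means one combined effect, that rests on III vs I. Both are open and without a placebo, so the conclusion is the same.

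**The case against.** The best defence is that this is loose wording and hides nothing. The arms are set out plainly, no one who reads Section 6(d)(vi) would think Group I is blinded, and an open comparison with no intervention is an ordinary choice for a behavioural session. The description was probably taken from the extract-against-molasses comparison. All of that is fair, and it is why the remedy is wording. But 6(d)(i) does not say so, and a design statement tends to be repeated without the arm details beside it.

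A second defence is that the endpoints are fairly objective and that reporting belongs in the SAP. Heart rate is read from a device, although blood pressure is taken manually (Section 5). Measuring objectively limits observer judgement, but it does not stop a participant's own expectation from affecting the reading. No SAP can blind Group I or separate the molasses from the meditation, because the arms are fixed in the protocol.

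A reader might go further and infer that III vs II is not double-blind either, since the student assistants take the readings, help analyse the data, and are nowhere described as masked to group. The protocol does not support that. It asserts double-blinding, nothing in it contradicts this for III vs II, and coded forms are consistent with it: "This code will be placed on both their initial questionnaire, inclusion/exclusion checklist, BP and HR readings, and their adverse events survey". A code does not itself prove masking, but how masking is done is undescribed operational detail and not a shown error. The same goes for whether the two spoonfuls look and smell alike.

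**Conclusion.** The statement in 6(d)(i) is wrong as written for two of the three comparisons, including both that bear on meditation. It can stand for III vs II, so the Passiflora comparison keeps its placebo control and its stated blinding.

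The trial is not uninformative about meditation. II vs I remains a randomised comparison, but it estimates the effect of meditation plus molasses plus awareness of treatment against nothing. III vs I adds Passiflora to that package. Neither isolates meditation.

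The count of comparisons follows directly from the arms. The participant counts (15 of 45, 20 of 60, about 23 of 70) assume equal allocation and show only the size of the arm that cannot be blind. A reader might want to turn this into a size of bias or a false-positive rate. The protocol gives no figure for a placebo, expectancy or observer effect, so none is claimed.

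**What to change.** 1. Restate 6(d)(i) along these lines: 'This will be a randomized, three-arm trial. The comparison of Group III with Group II is double-blind and placebo controlled. Comparisons with Group I are open to participants and not placebo controlled.'
2. Interpret II vs I as meditation plus placebo against no intervention, and III vs I as Passiflora plus meditation against no intervention. Attribute neither to meditation alone.

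This needs no added participants, measurements, staff or material. The price is that the trial gives up the double-blind, placebo-controlled claim for two of three comparisons, and with it any claim about meditation in isolation. Isolating meditation would need a different control arm. That is a redesign, and it is not needed to make the design statement true.

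### The minute-30 app cut-off for withdrawal does not fit the reading schedule: a participant whose app starts late can stay in, yet cannot finish the 10-minute meditation before the second reading

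*Protocol*

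**What the plan says.** Protocol section 6(d)(iv) sets the readings "taken 15 minutes after the end of the exam and then 15 minutes after that". Under section 6(d)(vi), the placebo and meditation in Group II are timed "15 minutes after classroom examination", and the extract and meditation in Group III "15 minutes after examination". The meditation lasts 10 minutes in both groups. Item (c) has the same wording in each group: "Three left arm seated blood pressure readings and one heart rate will be taken 15 minutes after the baseline reading". Section 6(d)(vii)(3) repeats the 15-minute interval and puts the whole session at about 45 minutes.

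Section 6(g)(iii) lists grounds for removal and opens with "Withdrawal may occur without the" participants' consent. The first ground is "His/Her smartphone or Headspace application is not functioning within 30 minutes after the end of his/her classroom examination". Under section 6(g)(ii), the data of a withdrawn participant are left out of the analysis.

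Three provisions make app failure less likely. Section 6(d)(v) states "All participants will be instructed to download Headspace app onto their smartphone prior to the research date". Section 6(b) requires a smartphone with access to the app, and headphones, and excludes those without the phone or the app. Section 7(e)(i) promises detailed instructions in advance (Attachment E). For Group I, item (b) says "This group will not be given any intervention", so that group does not use the app during the session.

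**The concern.** The withdrawal ground and the reading schedule run on the same clock but do not fit. The app may start working as late as the minute of the second reading without triggering the ground, whereas a complete meditation needs a start 10 minutes before that. Anyone in between has no listed reason to be removed, and no section delays the reading for a late start.

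Blood pressure and heart rate are the primary endpoints, and the meditation is part of both active arms. A participant read during the meditation, or before it begins, would contribute a value that does not reflect the full intervention. This would tend to pull Groups II and III towards Group I.

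The rule also works unevenly. Group I never opens the app during the session, so a failure there may go unnoticed. Removals on this ground, with the loss of data under section 6(g)(ii), would in practice fall on Groups II and III.

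**Working it through.** **Inputs from the protocol** (minutes after the end of the exam)
- Baseline: 15 (6(d)(iv) and 6(d)(vi), item (a))
- Interval from baseline to second reading: 15 (6(d)(iv); 6(d)(vi), item (c); 6(d)(vii)(3))
- Length of meditation: 10 (6(d)(vi), item (b), Groups II and III)
- App cut-off: 30 (6(g)(iii)(1))

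**Nominal schedule**
- Second reading: 15 + 15 = minute 30.
- On-time session: 15 + 10 = minute 25, which leaves 5 minutes before the reading.
- Latest start that finishes by the reading: 30 − 10 = minute 20.
- Gap between that start and the cut-off: 30 − 20 = 10 minutes.

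**Meditation completed at the minute-30 reading**, for a start at minute s: min(10, 30 − s)

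| App first works (s) | Minutes done at reading | Withdrawal ground met? |
|---|---|---|
| 20 | 10 of 10 | no |
| 21 | 9 of 10 | no |
| 25 | 5 of 10 | no |
| 28 | 2 of 10 | no |
| 30 | 0 of 10 | no |

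**If baseline is late**, at minute b, the reading is at b + 15 and the latest workable start at b + 5. The gap to the cut-off is 30 − (b + 5) = 25 − b: 10 minutes at b = 15, 5 at b = 20 and 0 at b = 25.

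**If staff held the reading instead**, a start at minute 30 would end at minute 40, which is 40 − 15 = 25 minutes after baseline. That fits within about 45 minutes but breaks the 15-minute interval.

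**Weight of one participant**, assuming three equal groups (no ratio is stated): 1/(70/3) = 4.3% of a group at 70 subjects, 1/(60/3) = 5.0% at 60 and 1/(45/3) = 6.7% at 45. If individual effects are similar, and a late starter's effect lies between none and full, each such person lowers the group's mean effect by at most that share.

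**The case against.** The strongest reply is that this is an unaddressed edge case. The withdrawal wording is permissive and sets an outer limit for removing someone. It does not say that a minute-29 starter is to be kept and read on time. Such a person already departs from the procedure, and the handling of departures can be left to a statistical analysis plan, which is not at hand. The harm also needs several things together: the app fails at the planned start, recovers only after minute 20, the participant is not withdrawn, and the reading is taken before the session ends. Advance download, the eligibility criteria and Attachment E all make this less likely. Attachment E is not shown and may already include an app check.

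The points on frequency stand, and they keep this minor. The rest does not close the gap. The discretion applies to the listed grounds, and none covers an app that starts late but by minute 30. The 45-minute session does not authorise a later reading, because the same item repeats the 15-minute interval. The cut-off and the schedule are both fixed in the protocol, so their mismatch is not a matter of later analysis detail.

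Two limits on the effect also stand. In Group III the extract is timed separately from the app, so a late app costs the meditation component only. And since Groups II and III both use the app, failure should be unrelated to assignment between them, so the comparison of II with III is less exposed.

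**Conclusion.** The point holds as a minor one. On the nominal schedule the cut-off is 10 minutes later than the latest start that allows a complete meditation before the second reading. Participants whose app first works in that interval meet no withdrawal ground and cannot complete the session on schedule. The likely consequence is dilution, mainly of Groups II and III against Group I, by at most 4.3% to 6.7% of a group's mean effect per affected participant under the assumptions shown. How many would be affected cannot be estimated from the protocol; probably few.

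The result treats baseline as a single time, because no duration is given for the readings. The 10-minute figure assumes baseline at minute 15, and the gap closes if baseline slips to minute 25.

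A reader might go further. The intervention is timed from the exam and the follow-up from baseline, and section 5 lists five cuffs and one pulse oximeter for sessions of 15–25 students. One might infer that some baselines would be taken after the intervention. The protocol does not support this. The label of item (a) and the order (a), (b), (c) place baseline first, no common end of the exam is stated, and no reading time is given from which to show that the schedule is infeasible. Timing slippage unrelated to group would add noise, not bias.

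**What to change.** Reconcile the cut-off in section 6(g)(iii)(1) with the schedule in section 6(d), so that nobody can stay in without time to finish the meditation before the second reading. One way is to confirm that each participant's phone and app work before the baseline reading. This should be done in all three groups, so that any removal for this reason does not depend on group. Which time should govern is for the investigators to decide.

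The cost is a change of wording and a brief check per participant, which may partly repeat what Attachment E already asks.

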anxiety (12-14) with mild and non-serious adverse effects, including headache, abdominal pain, and flatulence. Doses in these trials ranged from 260mg – 700mg. Rare side effects from chronic *Passiflora* use included vasculitis, asthma, rhinitis, and urticaria (15). One case study from 2000 revealed a toxic reaction to *Passiflora incarnata*, in which the patient experienced various cardiovascular effects, including ventricular tachycardia (16). Passionflower extract also contains harmine and hardline which may stimulate uterine contractions, and is therefore contraindicated in pregnancy. It has theoretical action as a platelet inhibitor, so it is contraindicated before surgery. A 2017 trial comparing *Passiflora incarnata* to midazolam before dental extraction found that both *Passiflora* and midazolam improved patients pre-procedure anxiety levels, and they concluded that the *Passiflora* was safe and effective in this one-time dosage (17). 50% of the participants in this trial experienced drowsiness as a side effect of the 260mg preoperative dosage. 20% experienced muscle relaxation, 5% experienced dizziness, 2.5% experienced an allergy, and 2.5% experienced epistaxis. A 2013 study evaluated the effects of 500mg *Passiflora incarnata* on anxiety levels before periodontal treatment. This study found significant reductions in anxiety in those taking the botanical extract with no reports of any adverse effects (18). Lastly, a 2001 study on 36 patients found comparative anxiolytic effects between *Passiflora* and oxazepam with mild-moderate dizziness, drowsiness, impairment of job performance, and confusion listed as the most frequent side effects for both interventions. In the *Passiflora* group, two participants experienced a mild-moderate allergic reaction and two participants experienced mild-moderate ataxia (19). There is no evidence in the current literature that *Passiflora* is an abortifacient or teratogen. To our knowledge, no recent human trials have been done to investigate the effects of *Passiflora incarnata* on blood pressure. A related plant, *Passiflora edulis* has demonstrated antihypertensive properties in rats (20, 21).

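### The risk text attributes adverse effects to chronic use and credits one-time dosing with reducing them, but its only three rates match those reported after a single dose

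*Protocol*

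**What the plan says.** Section 6(d)(vii)(4) lists the measures meant to lessen risk. Item (a), the first, says adverse events from *Passiflora incarnata* "use have been found with chronic dosage" and continues: "We attempt to minimize these risks by providing one-time acute dosage".

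Section 7(f)(ii) introduces its list by saying that studies "have generally found mild-moderate adverse effects when taken for weeks-months including" the items that follow. Three items carry a rate: "Drowsiness (very common, up to 50% reported this adverse effect in studies"), "Muscle relaxation (common, up to 20% reported this in studies"), and dizziness at up to 5%. Under each of these three, participants are advised to take care and to keep off driving and heavy machinery for an hour from dosing. Section 7(f)(iii) repeats the one-time-dose argument, but only for events arising from long-term use.

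Section 3 (Background) describes a 2017 dental-extraction trial whose authors concluded that the product "was safe and effective in this one-time dosage (17). 50% of the participants in this trial experienced drowsiness" after "the 260mg preoperative dosage. 20% experienced muscle relaxation, 5% experienced dizziness". It adds 2.5% with allergy and 2.5% with epistaxis. It ties a different set of effects to prolonged exposure: rare side effects from chronic "use included vasculitis, asthma, rhinitis, and urticaria (15").

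**The concern.** The risk text makes two linked statements: the adverse effects belong to chronic or weeks-to-months use, and giving one dose therefore reduces them. If the best-quantified effects in the list come from a single-dose trial, the first statement is wrong for them and the second does not follow. Anyone using this section to judge risk would take drowsiness, muscle relaxation and dizziness to be effects of prolonged use that the design largely avoids, when the protocol's own Background reports them after one dose.

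The practical stake is participant safety shortly after dosing. The measure that does address these three effects is the driving caution. As worded it names a fixed hour and does not ask whether symptoms have gone.

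**Working it through.** No sample-size or test formula applies. The check sets the two sections side by side.

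| Effect | Section 7(f)(ii), headed as weeks-to-months use | Section 3, trial of one 260 mg dose |
|---|---|---|
| Drowsiness | up to 50% | 50% |
| Muscle relaxation | up to 20% | 20% |
| Dizziness | up to 5% | 5% |
| Allergic reaction | listed with urticaria, no rate | 2.5% |
| Nosebleed | listed, no rate | 2.5% |

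1. **Match.** All three rates agree (50 = 50, 20 = 20, 5 = 5), and Section 7(f) contains no other percentage. The Background gives no other rates for these effects. Its 2001 comparison with oxazepam names drowsiness and dizziness as frequent, but gives neither a rate nor a duration of use.

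2. **What is tied to chronic use.** Only vasculitis, asthma, rhinitis and urticaria are, and without rates.

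3. **Consequence.** A rate observed after one dose cannot be expected to fall because only one dose is given. The argument in 6(d)(vii)(4)(a) can reach the four effects in step 2. It cannot reach the five in the table.

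4. **An entry that mixes both kinds.** Item (10) of 7(f)(ii) combines urticaria, tied to chronic use, with allergic reaction, reported at 2.5% after the single dose. The one-time-dose argument may apply to one half of that entry and not to the other.

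5. **Incidence in this trial.** Group III has 45/3 = 15 to 70/3 ≈ 23 participants if allocation is equal (an assumption; the protocol states no ratio). If the single-dose rates carried over in full, the expected counts would be:
   - drowsiness: 0.50 × 15 = 7.5 to 0.50 × 23 = 11.5
   - muscle relaxation: 0.20 × 15 = 3.0 to 0.20 × 23 = 4.6
   - dizziness: 0.05 × 15 = 0.75 to 0.05 × 23 = 1.15

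   The Background also describes a 500 mg trial before periodontal treatment with no adverse effects reported, so the lower end of each range is zero. The planned dose is nominally 900 mg, and the protocol does not say whether extract weights are comparable across products. These counts are the same whichever heading the list carries, so they give context and do not measure the misattribution.

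**The case against.** The strongest reply is that the text claims less than this point suggests. Section 7(f)(iii) is expressly limited to events from long-term use. The risks meant in 6(d)(vii)(4)(a) can be read the same way, and neither sentence names drowsiness, muscle relaxation or dizziness. The rates are given as upper limits, the introduction to the list is hedged, and the Background openly reports their single-dose origin. The driving caution runs from the dose, so the authors evidently treated these as acute effects. Other protections exist: the medication, food and alcohol exclusions, a same-day adverse event survey, follow-up of moderate to severe events, a contact number for later events, and health services in the building.

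Much of this stands. Section 7(f)(iii) is correct and can stay. But 6(d)(vii)(4)(a) speaks of adverse events of the product without distinction, and the heading of 7(f)(ii) places the three rated effects under prolonged use. The other protections leave that attribution uncorrected.

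Three stronger readings are tempting and are not supported:

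- A reader might infer that participants are unprotected against the three effects. They are not: the caution and the measures above apply.
- A reader might infer that one hour is too short. No document shows this. It can also be argued that the general advice to take care is not confined to the hour. What can be said is that the driving limit is fixed and not linked to symptoms.
- A reader might want a symptom check before participants leave, in Groups II and III only. Adverse events are the primary safety endpoint and every participant receives the same survey, so prompting two groups out of three would make ascertainment unequal.

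**Conclusion.** The point holds as an internal inconsistency in the risk description, of minor severity. Three of three rates in Section 7(f)(ii) are placed under weeks-to-months use while the Background reports identical figures after one 260 mg dose, and two further listed effects (allergic reaction and nosebleed) were also seen in that trial. One-time dosing therefore cannot be credited with reducing these five.

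This rests on one inference: Section 7(f) names no source for its rates, so their origin is deduced from the exact match. It does not rest on any assumed incidence at the study dose, which is unknown.

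A reader might take the expected counts of drowsy or dizzy participants as the size of the problem. The documents do not support that, since the counts run from zero up to the single-dose rates and would not change if the heading were corrected. The blood pressure and heart rate endpoints and the power statement are unaffected.

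**What to change.** 1. In Section 6(d)(vii)(4)(a), limit the one-time-dose argument to vasculitis, asthma, rhinitis and urticaria. State that drowsiness, muscle relaxation, dizziness, allergic reaction and nosebleed have been reported after a single dose.
2. Re-head Section 7(f)(ii) to match. Label the three rates *reported after a single 260 mg dose; not known at the study dose*, and list allergic reaction separately from urticaria. Section 7(f)(iii) needs no change.
3. Word the caution as: *no driving or heavy machinery for at least one hour after the dose, and for as long as any drowsiness, dizziness or muscle relaxation persists*.

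A symptom check before participants leave is optional. If one is wanted, apply it in all three groups so that adverse events are ascertained equally.

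The cost is a few lines of protocol wording, a slightly less favourable risk statement, and a possible delay before driving for participants who still have symptoms.
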